The use of pulmonary vasodilators will promote forward flow in the Fontan circuit, reduce hepatic congestion and halt the progression of liver fibrosis.

C. Innovation

(i) Available data suggest that chronic hepatic congestion, inherent in the Fontan physiology, is the precursor of early liver fibrosis and cirrhosis in the Fontan population.^{2,3} A recent study based on the Mayo Clinic Fontan

cohort showed that half of the patients had liver fibrosis after 30 years from the time of initial Fontan.⁶

(ii) This proposed study would be the first study to assess the role of pulmonary vasodilators in the management of FALD.

D. Significance

(i) The adult congenital heart disease program at Mayo Clinic has the largest and oldest cohort of Fontan patients in the United States, and this places Mayo Clinic in a unique position to study this problem.

(ii) Data from this study will influence the management of FALD nationally and worldwide.

E. Brief Synopsis of Methods

(i) All patients enrolled in the study will undergo a baseline liver magnetic resonance elastography (MRE) prior to the initiation of phosphodiesterase-5 inhibitor (sildenafil).

(ii) A second MRE will be performed after 12 months of therapy.

F. Preliminary studies to support feasibility

(i) Several studies have shown that the use of pulmonary vasodilators in Fontan patients (even those with normal pulmonary vascular resistance) results in increased cardiac output and exercise tolerance by promoting forward flow in the Fontan circuit.¹⁴⁻¹⁶

(ii) A recent study from the Mayo Clinic showed that liver stiffness measured by MRE correlates with severity of fibrosis on liver biopsy.¹³

(iii) The proposed study is built on the foundation of these previous studies. Pulmonary vasodilators will be used to promote forward flow in the Fontan

circuit, and thereby reduce liver congestion. MRE will then be used to monitor treatment effect. We chose a phosphodiesterase-5 inhibitor instead of an endothelin receptor antagonist because the latter is associated with hepatotoxicity.

G. Study design

1. Inclusion criteria: All adult (age \geq 18 years old) Fontan patients who have no contraindications for magnetic resonance imaging (MRI) will be eligible for the study. Informed consent will be obtained from potential participants by their primary cardiologist or dedicated study personnel.

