2. Exclusion criteria: Subjects with implantable pacemakers, residual cardiac lesions (severe ventricular dysfunction, severe atrioventricular valve regurgitation, Fontan baffle or conduit obstruction), viral hepatitis, severe renal dysfunction, a history of sildenafil use in the six months prior to study enrollment, ongoing sildenafil therapy, or patients currently taking nitrates. Based on the stipulation from the Food and Drug Administration regarding the approved use of sildenafil, we also excluded patients with hypotension at baseline (BP $<$ 80/50 mmHg), pulmonary veno-occlusive disease, and pulmonary hypertension due to sickle cell disease. Women of child-bearing potential with a positive pregnancy test will additionally be excluded.
3. All participants may undergo the following baseline tests (\pm 4 weeks) as part of standard clinical care: transthoracic echocardiogram, electrocardiogram, cardiopulmonary exercise test, complete blood count, chemistry panel, INR, alpha-fetoprotein. All these tests are routine clinical tests in the Mayo Clinic Adult Congenital Heart

- Disease program. Baseline clinical tests performed within 6 months prior to enrollment will be accepted as part of the study (data will be utilized if results are available). Any routine standard clinical tests or procedures that are not completed will not be considered a deviation.
4. Other additional baseline tests include:
 - a. MRI studies: [cardiac MRI + Liver MRE + 4D phase contrast imaging of the abdomen]
 - b. Abdominal ultrasound [full abdominal scan with Doppler of portal/hepatic/mesenteric vessels]
 - c. Biomarkers [NT-proBNP, ST2, Galectin-3, ADMA, ceramides, hs-CRP, Cystatin C, electrolytes]
 - d. Quality of life indices: MLHFQ: Minnesota Living with Heart Failure Questionnaire (for patients enrolled prior to protocol version 2, baseline MLHFQ will be administered at re-consent (+/-4 weeks).
 5. This will be a double blinded placebo control study design. All participants will be randomized 1:1 to sildenafil or placebo for a total of 12 months therapy.

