 6. Sildenafil will be initiated at 5 mg 3 times per day for the first week, and titrated to 10 mg 3 times per day for the second week and 20 mg 3 times per day from the 3rd week to the end of the study period. The patients will be required to check their pulse rate and blood pressure daily during the first month of drug therapy. Patient who experience hypotension (blood pressure < 90/50 plus symptoms such as dizziness) during dose titration will be asked to remain on the previous tolerated dose. Patients who cannot tolerate 10 mg 3 times daily will be asked to withdraw from the study and will be asked to

- continue checking their blood pressure for three days after stopping the medication.
7. After 12 months (+/- 4 weeks) of therapy, all tests listed in #3 and #4 will be repeated.
 8. These same tests listed in #3 and #4 will be repeated for the patients who have follow-up up to 24 months (+/- 4 weeks).
 9. Adverse event and compliance monitoring: During the first month of enrollment (initiation and dose titration), adverse events will be collected by subject report and by weekly telephone or email interview (± 7 days) with dedicated research personnel. For the rest of the study period, adverse events will be collected by subject report and by monthly telephone or email interview (± 14 days) with dedicated research personnel. The research personnel will be responsible for sending out the monthly supply of medications and obtaining a count of the remaining number pills as a measure of compliance. All participants will be provided with a pamphlet containing all the side effects of sildenafil, and contact information of research team for reporting any adverse event or concerns about the study.
Up to three voicemail messages will be left for each follow-up.

H. Statistical analysis and power considerations:

Sample size and power

We have determined that a total of 40 patients who complete the study (20 patients in the treatment arm and 20 patients in the placebo) will adequately power the study accounting for approximately a 10% attrition rate. In a prior

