study from the Mayo Clinic,¹³ the distribution of MRE stiffness score in the adult Fontan population was $4,900 \pm 1,100$ Pa. Assuming that the standard deviation of MRE is 1,000 both for before and after treatment measures, and that the within subject correlation between before and after measures is at least moderate in strength and positive (i.e. $\rho \geq 0.5$), then the variance in the difference between pre- and post-treatment MRE stiffness score is no more than 250 Pa. A sample of 40 patients in the treatment arm will provide 80% power for a two-sided two-sample t-test with a 0.05 Type I error rate to detect a mean difference of at least 500 Pa in treatment effect, as measured by the difference within patient MRE stiffness score.

Interim Analysis

An interim analysis of subjects who have completed 12 months of Sildenafil vs. Placebo therapy will be conducted at the end of the grant period (August 2019). Those still on Sildenafil vs. Placebo at that time will remain blinded until their completion of 12 months on Sildenafil vs. Placebo.

I. Human studies issues (consent or research authorization)

Consent

An informed consent will be obtained from the patients at the time of enrollment in the study. The consent will authorize a member of the research team to contact each patient by phone, email, or questionnaire. The study participants will be notified of the very limited evidence supporting the use of sildenafil in this population.

Data and Safety Monitoring

The Food and Drug Administration approved Sildenafil for the treatment of pulmonary hypertension. The patients will be notified that the use of sildenafil in this study is off-label. We will implement an internal safety monitoring system consisting of two members (not immediately affiliated with the study) to review reported side effects of sildenafil at the mid-point and completion of the study. Finally, and as always, extreme caution and monitoring of study participants will be undertaken throughout the study and in follow up to ensure no untoward events as a direct result of the study substance. Please see data safety monitoring plan.

M. Literature cited

1. Fontan F and Baudet E. Surgical repair of tricuspid atresia. *Thorax*. 1971;26:240-8.
2. Rychik J. Forty years of the Fontan operation: a failed strategy. *Seminars in thoracic and cardiovascular surgery Pediatric cardiac surgery annual*. 2010;13:96-100.
3. Gewillig M. The Fontan circulation. *Heart*. 2005;91:839-46.

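### For patients still on therapy in August 2019, the guaranteed blind stops at 12 months on study drug, so it need not cover their 12-month tests or the reading of their MRE

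*Combined protocol and SAP*

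**What the plan says.** Section H (Interim Analysis) sets one look: "An interim analysis of subjects who have completed 12 months of Sildenafil vs. Placebo therapy will be conducted at the end of the grant period", dated August 2019. For everyone else it adds: "Those still on Sildenafil vs. Placebo at that time will remain blinded until their completion of 12 months on Sildenafil vs. Placebo". It gives no purpose, endpoint, test, alpha, decision rule or access rule for the look.

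The outcome tests are timed elsewhere:

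- E(ii): "A second MRE will be performed after 12 months of therapy".
- G.7: "After 12 months (+/- 4 weeks) of therapy, all tests listed in #3 and #4 will be repeated". The repeated set includes the liver MRE, the MLHFQ (G.4d: "Quality of life indices: MLHFQ: Minnesota Living with Heart Failure Questionnaire") and, where done, the cardiopulmonary exercise test (G.3).
- G.8 repeats the set at up to 24 months for patients with that follow-up.

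The length of dosing is described in two ways. G.5 has "All participants will be randomized 1:1 to sildenafil or placebo for a total of 12 months therapy". G.6 continues the final titration step "from the 3rd week to the end of the study period".

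G.5 calls the design double blind. It does not say when the blind ends, who is blinded, or whether MRE readers are blinded.

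**The concern.** A blind protects an outcome only if it lasts until that outcome has been measured and read. Here the written guarantee is attached to time on study drug, while the measurements come after it.

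A patient who learns the assignment before the 12-month visit may answer the MLHFQ differently or try harder, or less hard, on the exercise test. Staff who know it may coach or score differently. MRE stiffness, the outcome used for the sample size, is less open to this because it does not depend on patient report or effort. It still has to be read, and the documents do not say that the reader is kept blind.

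**Working it through.** **No stated figure to reproduce.** The documents give no number for the length of the blind or for the error rate across looks. The 80% power statement in section H does not bear on this point.

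**Step 1: the end of the blind against the tests.**

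| Event | Timing in the text | Source |
|---|---|---|
| Guaranteed blind ends | 12 months on study drug | H, Interim Analysis |
| Second MRE | after 12 months of therapy | E(ii) |
| All repeat tests | 12 months of therapy, 4 weeks either side | G.7 |
| MRE reading | not stated | – |
| Later tests | up to 24 months, 4 weeks either side | G.8 |

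**Step 2: size of the gap.** Gap = date of test minus date on which 12 months of therapy is completed.

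- *Dosing stops at a fixed 12 months (G.5) and the window belongs to the tests.* The latest permitted test is at 12 months + 4 weeks, so the gap is at most 4 weeks. Tests done before the 12-month point have no gap.
- *Dosing runs to the visit (G.6) and the window belongs to the therapy.* The tests and the end of therapy roughly coincide, so the gap is about 0. Even then, release is not tied to completed tests or to a read scan.

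The range is 0 to 4 weeks per patient. This is a calendar width and not an estimate of bias. Any further interval until the MRE is read cannot be sized, because no reading time is given.

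**Step 3: delay from holding results until the last patient is done.** Assume that the look is on 31 August 2019 and that nobody starts therapy after it (no enrolment end date is given). The last possible 12-month point is 31 August 2020, 366 days later. Adding 28 days gives 28 September 2020: 366 + 28 = 394 days, about 13 months, plus time for reading and lock.

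**Step 4: the secondary clarification.** Suppose, contrary to anything stated, that arms are compared at both looks and either may support a claim at two-sided 0.05. With information fraction *t* at the first look, the two test statistics have correlation √*t*, and overall error = 1 − P(|Z₁| ≤ 1.96 and |Z₂| ≤ 1.96). The documents do not give *t*, so a range is assumed:

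| Assumed *t* | √*t* | Overall error | Excess over 5% (percentage points) |
|---|---|---|---|
| 0.25 | 0.50 | 9.1% | 4.1 |
| 0.50 | 0.71 | 8.3% | 3.3 |
| 0.75 | 0.87 | 7.3% | 2.3 |
| 0.90 | 0.95 | 6.5% | 1.5 |

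If the look is pooled or descriptive, with no claim from it, the error of the final test stays at 5%.

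**The case against.** The best case for the plan has four parts.

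**The sentence protects the blind.** It says how long ongoing patients stay blinded at least. It does not say that codes are opened on that day, or to whom. This stands. A reader might infer a planned breach, or that the codes of patients who had already finished are opened in August 2019. The text states neither. What remains is that the guarantee stops too early.

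**The natural reading of G.7 may leave no gap.** The window sits inside the phrase about duration of therapy, and G.6 runs dosing to the end of the study period. On that reading the tests and the end of therapy coincide. This also stands, and it is why the range starts at 0. G.5 supports the other reading, though, and a blinding rule should not depend on which one the site adopts.

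**The main outcome is less exposed.** Only MRE stiffness has a stated test. The MLHFQ and the exercise test have no stated analysis, and the exercise test is optional: "Any routine standard clinical tests or procedures that are not completed will not be considered a deviation". This limits the weight of the point without removing it.

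**The look is not shown to inflate error.** A reader might infer that the plan spends alpha twice. The documents state no test at the look, no claim from it and no stopping rule, so this is missing detail and not an error in the plan.

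Section I also refers to a separate data safety monitoring plan, which is not among the documents. It may contain access rules; this could not be checked.

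**Conclusion.** The point holds as a weakness in a stated rule. For patients still on therapy in August 2019, the written guarantee of blinding need not cover the 12-month tests or the MRE reading. The general double-blind statement in G.5 does not fill the gap, because it gives no end point.

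The possible exposure before testing is 0 to 4 weeks per patient. It would occur only if assignments are in fact released at 12 months on drug and a test or reading follows. Its effect on results cannot be estimated from the documents. It is of more concern for the MLHFQ and the exercise test than for MRE stiffness.

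The 6.5% to 9.1% range is conditional on by-arm testing with a possible claim at 0.05 at both looks, and on assumed information fractions. It shows why the status of the look should be written down; it does not describe what the plan does.

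The change should be made because it is cheap and removes an avoidable route to bias. Confidence is medium, given the two readings of G.7 and the unseen monitoring plan.

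**What to change.** **Minimum.** In section H, replace the 12-month limit on the blind with: *until their 12-month tests are completed (or recorded as not done) and their MRE has been read*. The words in brackets are needed because G.3 does not treat a missed routine test as a deviation.

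**Preferred.** Also withhold by-arm interim results from patients, staff in contact with patients and outcome assessors until the last patient's 12-month tests are done and the 12-month data are locked. Safety unblinding is unchanged.

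**Later tests.** State that any G.8 tests done after assignments are released, up to 24 months, will be reported as unblinded.

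**Consistency.** Reconcile G.5, G.6 and G.7 on when therapy ends relative to the 12-month visit.

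**Secondary clarification.** Add one sentence saying that the August 2019 look is descriptive, with no efficacy claim and no stopping, so that the final test keeps 0.05.

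**Cost.** A few sentences, no extra patients and no loss of final alpha. The minimum version delays a patient's assignment by at most 4 weeks plus reading time, if tests are done in window. The preferred version delays assignments and by-arm results to about 13 months after the look, plus reading and lock, if nobody starts therapy after it. The document is dated July 31, 2019 and the look is in August 2019, so the amendment must be made within weeks or the look must wait for it.
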